**Figure 1. Timing of CESM study**

**Figure 2. Digital mammogram with dense tissue shows an irregular mass in the posterior right breast (arrows). The CESM study shows this mass as well as three other areas of invasive cancer between the mass and the nipple.**

At UVa, about 15 CESM studies are performed per month. The majority are performed for a diagnostic indication such as an abnormal mammogram or MRI, and less are performed for screening. However, screening CESM is often used for women at high risk that cannot undergo breast MRI for various reasons. Nationally, CESM has been slow to be adopted for screening despite the apparent high sensitivity. It is unclear if this is due to lower convenience, concern about IV placement or contrast reaction, or lack of knowledge of this test. The aim of this study is to evaluate patient attitudes related to the use of CESM as a breast cancer screening test.

### **Hypothesis to be Tested**

CESM is an emerging modality that is FDA approved for clinical use. It is possible that this functional test may someday replace breast MRI. While only small studies have been performed to date, one study has demonstrated similar cancer detection, sensitivity, and specificity for CESM compared with breast MRI (6). CESM could be an ideal screening examination for women with dense tissue.

### **Study Design: Biomedical**

**1. Will controls be used? No**

**2. What is the study design?**

- a) Evaluate the patient experience during a screening CESM to better understand if women find the experience of contrast injection to be too invasive or unpleasant to repeat or recommend to a friend. (“Pre-CESM” and “Post CESM” Surveys)

**3. Does the study involve a placebo? No**

### **Human Participants**

**Ages:** 40-69

**Sex:** female

**Race:** all

**Subjects- see below**

**INSTRUCTIONS:** For question 1-4 below insert an exact #. Ranges or OPEN is not allowed. This # should be the maximum # you expect to need to enroll (i.e. sign consent) If you are only collecting specimens the number of participants should equate to the # of specimens you need. If you are collecting only data from a chart review the number should designate the number of subjects whose medical records you plan to review. Age/ Sex/Race criteria should designate the demographics of participants from whom you will obtain the specimen/data.

**1. Provide target # of subjects (at all sites) needed to complete protocol.**

- 210 CESM procedures at the Breast Care Center.

**2. Describe expected rate of screen failure/ dropouts/withdrawals from all sites.**

CESM rates will be negligible due to pre-screening and study procedure involving only one visit.

**3. How many subjects will be enrolled at all sites? 210 for CESM at BCC;**

**4. How many subjects will sign a consent form under this UVa protocol? 210 for CESM**

**5. Provide an estimated time line for the study.**

Total 22 months. Enrollment 18 months followed by completion and data analysis

### **Inclusion/Exclusion Criteria**

**1. List the criteria for inclusion for CESM**

- Female
- 40 to 69 years
- Previous normal mammogram (BI-RADS 1 or 2) showing heterogeneous or extremely dense breast tissue within last 24 months
- Scheduled for screening mammogram as part of the patient's clinical care

**2. List the criteria for exclusion for CESM**

- No mammogram within last 24 months
- Fatty or scattered fibroglandular tissue on last mammogram
- History of allergy to iodinated contrast
- History of renal disease or renal function abnormalities
- Pregnant women
- History of diabetes

- History of paraproteinemia syndromes such as multiple myeloma
- History of collagen vascular disease
- History of vascular disease (coronary artery disease, myocardial infarction, carotid disease, peripheral vascular disease, or known visceral artery disease)
- Previously identified as high risk for breast cancer (>20% lifetime risk)
- Asthma
- Sickle Cell Anemia
- Currently on Dialysis
- If patient is age 60-69 years we will need to confirm that kidney function is normal. We will draw a small volume of blood and check this, unless patient has had a lab test showing normal kidney function in the last 30 days as part of standard of care.

**4. List any restrictions on use of other drugs or treatments.** none

### Statistical Considerations

**1. Is stratification/randomization involved?** No

**2. What are the statistical considerations for the protocol?**

There are no specific statistical considerations. We are only planning to evaluate women's experience and willingness to undergo CESM in the screening setting. However, it should be noted that if modifications are made to the general survey questionnaire (IRB Submission #11378) after the first 50 patients have completed the questionnaire.

**3. Provide a justification for the sample size used in this protocol.**

We have funding for 210 screening CESM subjects. This should allow us to evaluate for general attitudes toward CESM as well as some sub-analyses related to factors such as age, and family history. More specifically, we should be able to estimate the percentage of women who have a positive attitude toward CESM within  $\pm 3.5$  percentage units. This includes the worst case scenario in which the percentage is 50%, which is the scenario in which a binomial outcome variance is maximized.

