**4. What is your plan for primary variable analysis?**

1. To evaluate the patient experience during a screening CESM to better understand if women find the experience of contrast injection to be too invasive or unpleasant to repeat or recommend to a friend.

**Data summarization:** Pre and post CESM survey responses that are binary or Likert scaled responses will be summarized by frequencies and percentages. Pre and post CESM survey responses that are continuous scaled responses will be summarized by the mean and standard deviation, the median and interquartile range, and the range of distribution.

**Statistical analyses:** Pre CESM procedure survey information will be utilized to predict: (a) if patients who undergo CESM are willing to have repeat CESM, and (b) if patients who undergo CESM would recommend CESM to a friend. Multivariate logistic regression will be used to predict these two outcomes. In the former case (a), the outcome variable will indicate if the patient was willing to have a repeat CESM, and in the latter case (b), the outcome variable will indicate if the patient would recommend CESM to a friend. The multivariate logistic regression model predictor variables will include age, level of education, and breast cancer related risk factor variables. Type III Wald tests will be conducted to determine which predictor variables are uniquely associated with outcome. A  $p \leq 0.05$  null hypothesis rejection rule will be used as the bases for identifying unique partial associations.

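### The ±3.5-point precision claimed for 210 women equals one standard error; at the stated 50% worst case the 95% margin is ±6.8 points

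*Protocol*

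**What the plan says.** Item 3 of Statistical Considerations first gives the budget as the reason for the sample size: "We have funding for 210 screening CESM subjects". It then says the study can support "some sub-analyses related to factors such as age, and family history", and makes one numerical claim: "we should be able to estimate the percentage of women who have a positive attitude toward CESM within" ±3.5 percentage units. The claim is explicitly extended to the least favourable case: "This includes the worst case scenario in which the percentage is 50" per cent, "which is the scenario in which a binomial outcome variance is maximized".

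The item names no confidence level and does not call the figure a standard error. The only error rate in the protocol is the p ≤ 0.05 rule for the Wald tests in the logistic regressions (items 4 and 5).

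**The concern.** Saying that a percentage can be estimated within plus or minus some amount is the language of a margin of error, and most readers would assume 95% confidence. For 210 women and a percentage near 50%, ±3.5 points is far too narrow for that.

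The figure matters because it is the only quantitative argument offered for the sample size. It also concerns what the study is for, since the Background gives patient attitudes toward CESM as the aim. An ethics board or a later reader would believe the main descriptive result to be nearly twice as precise as it will be. The sub-analyses promised in the same item would be less precise still.

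**Working it through.** **Inputs**

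- n = 210, from item 3. No allowance for losses is needed on the protocol's own expectation for screen failures and dropouts: "CESM rates will be negligible due to pre-screening and study procedure involving only one visit".
- p = 0.50, the worst case named in item 3.
- Binomial variance p(1−p)/n, as item 3 implies.
- Confidence level: not stated. I assume 95% two-sided, in line with the p ≤ 0.05 rule in item 4 ("null hypothesis rejection rule will be used as the bases for identifying unique partial associations"), and also show 80% to 99%.

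**1. Reproducing the stated figure**

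SE = sqrt(0.50 × 0.50 / 210) = 0.0345, or 3.45 points, which rounds to 3.5. Working backwards, 0.25 / 0.035² = 204.1, so 205 women, close to 210. The figure is reproduced with a multiplier of 1.

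**2. Margin at usual confidence levels** (z × 3.45 points)

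| Confidence (two-sided) | z | Margin (points) |
|---|---|---|
| 80% | 1.282 | ±4.42 |
| 90% (or one-sided 95%) | 1.645 | ±5.68 |
| 95% | 1.960 | ±6.76 |
| 99% | 2.576 | ±8.89 |

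None gives 3.5. The 95% margin is 6.76 / 3.5 = 1.93 times the stated figure.

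**3. Other 95% methods at 105/210**

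Wilson gives ±6.70, the continuity-corrected interval ±7.00, and Clopper-Pearson 43.0% to 57.0% (±6.96). The choice of method does not explain the gap.

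**4. What ±3.5 points delivers**

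0.035 / 0.0345 = 1.014, and 2Φ(1.014) − 1 = 0.690. The exact binomial probability that the observed percentage falls within 3.5 points of 50% is 0.699. Coverage is therefore about 70%.

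**5. Women needed for a true ±3.5 at 50%**

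n = z² × 0.25 / 0.035² gives 784 at 95%, 553 at 90% and 336 at 80%.

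**6. Where ±3.5 would hold at 95% with 210 women**

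This requires p(1−p) ≤ 210 × (0.035/1.96)² = 0.0670, so p at most about 7.2% or at least about 92.8%. These limits use the simple normal-approximation (Wald) interval.

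**7. Finite-population correction**

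Solving 6.76 × sqrt((N − 210)/(N − 1)) = 3.5 gives N of about 286. The correction rescues the figure only if the whole target population is about 286 women, which nothing in the protocol suggests.

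**8. Subgroups**

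The protocol gives no subgroup sizes. As an illustration, half the sample (105 women) gives 1.96 × sqrt(0.25/105) = ±9.6 points at 95%.

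**The case against.** The strongest reply is that the protocol never says 95%, confidence interval or margin of error. The number follows correctly from its own inputs as a standard error, so the fault is a missing label more than a wrong calculation. It is true that 95% is a convention here and not a quoted input. The p ≤ 0.05 rule applies to the regression tests and does not fix a level for estimation. It is also true that the one-standard-error origin is inferred from the arithmetic, because no derivation is shown. Neither point rescues the sentence. Every level from 80% to 99% gives ±4.4 points or more, and a standard error presented as the distance within which a percentage will be estimated still needs correcting.

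A second reply is that little depends on the figure. The budget set the sample size, no decision rule or planned test uses ±3.5, and intervals computed from the data will not inherit the error. That stands, and it limits the harm to the justification itself. But this is the only number in that justification, and it fails at the very scenario it names.

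Two narrower points also stand. The half-sample subgroup is the reviewer's illustration, since nothing says age or family history would split the women evenly. The 7.2% and 92.8% limits depend on the method: at 195/210 (92.9%) the half-width is 3.48 points by Wald but 3.54 by Wilson. Neither changes the conclusion.

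**Conclusion.** The concern holds. With 210 women and a true percentage of 50%, ±3.5 points is one standard error, with about 70% coverage. The 95% margin is ±6.8 points (±6.7 to ±7.0 across methods), so the stated precision is about twice as good as the study can deliver. The result takes all 210 women as evaluable and treats them as a simple binomial sample, both in line with the protocol. The factor of two assumes 95% confidence. That the figure is too narrow does not depend on that assumption, since no usual level gives it.

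The design is not invalidated. The error lies in the stated precision, not in the number of women or any procedure.

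**What to change.** Keep 210 women and replace the precision sentence in item 3, for example: *With 210 women, the two-sided 95% confidence interval for the percentage with a positive attitude toward CESM has a half-width of at most about 6.8 percentage points, reached when the percentage is 50%.*

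If precision in sub-analyses is to be mentioned, add a clause marked as illustrative: about 9.6 points in a subgroup of half the sample. Labelling 3.5 explicitly as the standard error would also be accurate, but it tells the reader less than an interval at a stated level.

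The cost is one sentence in the protocol. No extra women are needed and no procedure changes; the stated precision simply becomes less favourable.

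### The sample-size precision is stated for an undefined attitude percentage, while the two primary percentages carry no interval and the only primary inference is two regressions that 210 women were not sized for

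*Protocol*

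**What the plan says.** Protocol, Statistical Considerations, item 3 (sample size) begins with the budget: "We have funding for 210 screening CESM subjects". It then says what that number can deliver: "we should be able to estimate the percentage of women who have a positive attitude toward CESM within" ±3.5 percentage units. It extends the claim to the least favourable case: "This includes the worst case scenario in which the percentage is 50" per cent. It also expects the number to allow "some sub-analyses related to factors such as age, and family history", without a calculation.

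Item 4 (primary variable analysis) sets the primary aim: "if women find the experience of contrast injection to be too invasive or unpleasant to repeat or recommend to a friend". Under data summarization it says: "Pre and post CESM survey responses that are binary or Likert scaled responses will be summarized by frequencies and percentages". No interval is mentioned there. Under statistical analyses the two outcomes are willingness to have a repeat CESM and willingness to recommend it, and "Multivariate logistic regression will be used to predict these two outcomes". The "predictor variables will include age, level of education, and breast cancer related risk factor variables". Each predictor is judged by a Type III Wald test at p ≤ 0.05. Item 4 contains no other primary test or decision rule.

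**The concern.** Items 3 and 4 of the same section do not meet. Item 3 states precision for a percentage that is not tied to a survey item, a response cut-off or a named outcome. Item 4 puts all its formal inference into regressions for which item 3 gives no odds ratio, power, outcome frequency or number of predictors.

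The aim is a question of how many: what share of women would repeat or recommend the examination. The regressions answer a question of who: which characteristics go with willingness. A single-group study of 210 answers the first question well. How well it answers the second depends on the size of the smaller outcome group, which may be small because every woman surveyed has already agreed to undergo CESM.

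At stake is the emphasis of the primary result. As written, the formal conclusion is a list of predictors below or above p = 0.05, and the percentages that address acceptability stand beside it without a statement of uncertainty.

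**Working it through.** **Inputs.** From the protocol: n = 210, worst case 50%, stated precision ±3.5 points (item 3); p ≤ 0.05 per predictor (item 4); negligible dropout (Human Participants, item 2). Not in the protocol, hence assumed: the share willing (50%, 80%, 90%, 95%), 80% power, and a two-sided test.

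**Step 1: the plan's own figure.** The standard error at 50% is √(0.5 × 0.5 / 210) = 0.0345, or 3.45 points. So ±3.5 is one standard error, equivalent to about 69% confidence. The 95% margin is 1.96 × 3.45 = 6.76 points. A 95% margin of ±3.5 at 50% would need 1.96² × 0.25 / 0.035² = 784 women.

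**Step 2: precision of a primary percentage with 210 women.** 95% margin = 1.96 × √(p(1 − p)/210):

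| Share willing (assumed) | 95% margin | 95% Wilson interval |
|---|---|---|
| 50% (105/210) | ±6.8 points | 43.3 to 56.7% |
| 80% (168/210) | ±5.4 points | 74.1 to 84.8% |
| 90% (189/210) | ±4.1 points | 85.2 to 93.4% |
| 95% (200/210) | ±2.9 points | 91.5 to 97.4% |

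A 95% margin of ±3.5 is reached only when the share is about 93% or more. All four intervals are still useful answers to the stated aim.

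**Step 3: what the regressions can detect.** Unwilling women = 210 × (1 − p). For a continuous predictor, the detectable odds ratio per SD is exp[(1.96 + 0.84)/√(210 × p(1 − p))]. For a 50/50 factor, I used a two-proportion normal calculation with 105 against 105 women, a pooled null variance, and the overall share willing held at p. At 90%, for example, 80% power needs 84.2% against 95.8% willing. The odds ratio is then (0.958/0.042)/(0.842/0.158), about 4.2 from the unrounded values.

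| Share willing (assumed) | Unwilling women | Odds ratio per SD | Odds ratio, 50/50 factor |
|---|---|---|---|
| 50% | 105 | 1.5 | 2.2 |
| 80% | 42 | 1.6 | 2.7 |
| 90% | 21 | 1.9 | 4.2 |
| 95% | about 10 | 2.4 | about 12 |

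These are unadjusted. Correlation among age, education and risk factors raises them: at 90% willing, an R² of 0.2 with the other predictors moves the per-SD value from 1.9 to 2.1. The normal approximation is rough in the last row, which shows scale only.

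**The case against.** - **The number comes from funding.** This stands. The precision sentence describes what the funded number can deliver and did not set it, so the document does not support saying that the sample size was derived from positive attitude.
- **Positive attitude may be lay wording for the primary outcomes.** The background section states the aim as evaluating patient attitudes, and item 4 reports a percentage for every binary or Likert item. A reader might infer that the sized quantity is never estimated. That goes too far: a point estimate of any such item is planned, and the surveys are not in the document. What stands is that the term is undefined and not linked to the two outcomes.
- **An interval method is a matter for the statistical analysis plan.** Taken alone, yes. The point does not rest on it. The protocol itself fixes which quantity gets a precision statement and which analyses carry the primary inference, and a plan that follows item 4 inherits the mismatch.
- **A null regression would leave acceptability unaddressed.** A reader might infer this, but the percentages are reported under the primary analysis whatever the regressions show. They lack stated uncertainty and primary rank.
- **The regressions may be adequate.** If about half the women are willing, the detectable odds ratios of 1.5 per SD and 2.2 for a balanced factor are moderate. The weakness depends on high willingness, which the protocol does not forecast. The mismatch remains at any level of willingness.

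**Conclusion.** The point holds in this form: item 3 supports 210 by the precision of a percentage that item 4 does not name, and item 4 gives primary inference to two regressions without a size basis while the percentages that answer the aim are only described. The regressions are reasonably informative near 50% willing and become weak at 90% or above, where 21 or fewer women would be unwilling and a balanced factor would need an odds ratio of about 4 or more. Those figures rest on assumed willingness, 80% power and unadjusted approximations.

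The ±3.5 in the same sentence is one standard error. The 95% margin in the stated worst case is about twice as wide, at ±6.8 points. This result depends only on n = 210 and 50%. The study remains worthwhile at its funded size; the matter should be corrected before analysis and does not call its feasibility into question.

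**What to change.** In item 3, replace positive attitude by the two item 4 outcomes, the percentage willing to repeat CESM and the percentage who would recommend it, and say which survey responses count as yes. Replace ±3.5 by the 95% margin for 210 women: about ±6.8 points at 50%, ±5.4 at 80% and ±4.1 at 90%.

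In item 4, make these two percentages, each with a two-sided 95% Wilson interval, the primary result. Keep the two logistic regressions as supporting analyses of who is willing.

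The cost is protocol wording and two intervals, with no new patients or data. The regressions rank lower than before, and the stated precision is less favourable than the one it replaces.

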**7. Will data from multiple sites be combined during analysis? No**

## Biomedical Research

**1. What will be done in this protocol?**

- Women age 40-69 years of age scheduled to undergo a screening mammogram at any one of our screening sites (Northridge, Orange, Zion Crossroads) or the UVa Breast Care Center will have their previous mammogram screened to see if there is evidence of heterogeneous or dense breast tissue (within 2 years). If so, the study nurse will contact the patient to see if they would like to participate in the CESM study. All patients having a CESM will have an appointment scheduled at the Breast Care Center, where CESM will be performed.
- In addition, study flyers approved by the IRB will be placed at UVa Imaging sites as well as primary care and gynecology offices.
- All women will have a urine pregnancy test at the Breast Care Center unless there has been no menstrual cycle for at least one year (postmenopausal) or history of hysterectomy.
- CESM is a mammogram performed after the injection of contrast via IV. Two images are taken almost simultaneously during the exam after the contrast is administered. The first image is essentially a standard mammogram. The 2nd image shows areas that take up the contrast (enhance) signifying increased blood flow. CESM studies are performed at the UVa Breast Care Center in the West Complex. Contrast administration is given following the same protocol of IV iodinated contrast administration as for CT scans elsewhere in the UVa Health System. Radiologists and technologists in the UVa Breast Care Center are trained in contrast administration and treatment of contrast reaction. Women having a CESM will have a 30 minute period post procedure to monitor for allergy to iodine contrast as per department SOP.
- Per department protocol, women age 60-69 will have serum creatine/GFR within 30 days or will have the test done prior to the CESM exam. If blood needs to be drawn prior to exam a BCC nurse or research nurse will draw 1 green top tube and send this to the Radiology Nursing area in main hospital. The blood will be processed for Creatinine and GFR on the I-STAT machine, results will be reported back to BCC. The standard mammogram portion of the CESM will be billed to the patients insurance as per standard of care. The administration of contrast and any cost related to the contrast enhanced portion of the CESM, will be paid for by the research study.

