**2. List the procedures, in bullet form, that will be done for RESEARCH PURPOSES as stipulated in this protocol.**

- Contrast-enhanced Spectral Mammography (CESM) at Breast Care Center
- CESM pre and post surveys for women having CESM procedure only
- Urine pregnancy test for all pre-menopausal women having a CESM at the BCC.

**3. Will you be using data/specimens in this study that were collected previously, with the use of a research consent form, from another research study? No**

**4. Will any of the procedures listed in item # 2 have the potential to identify an incidental finding? This includes ALL procedures, assessments and evaluations that are being done for RESEARCH PURPOSES that may or may not be considered investigational.**

Yes. Although the anticipated enhancing lesions are expected to have a high incidence of carcinoma, benign lesions may enhance as well that would not be otherwise detected.

X The examination(s) utilize(s) the same techniques, equipment, etc., that would be used if the subject were to have the examination(s) performed for clinical care. **There exists the potential for the discovery of clinically significant incidental findings.**

- The PI takes full responsibility for the identification of incidental findings:
- The PI will inform the subjects verbally of all incidental findings that are of clinical significance or are of questionable significance.
- A follow-up letter describing the finding should be provided to the subject with instructions to either show the letter to their PC or if the subject has no PCP, the subject should be instructed to make an appointment at UVa or at the Free Clinic.

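### The sample-size text promises the percentage of women positive toward CESM, but only women who accepted and had CESM are surveyed, and the stated margin does not cover that selection

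*Protocol*

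**What the plan says.** The Protocol, Statistical Considerations, item 3, starts from the budget ("We have funding for 210 screening CESM subjects") and states what that number buys. First: "This should allow us to evaluate for general attitudes toward CESM", together with some subgroup analyses. Then, more precisely, "we should be able to estimate the percentage of women who have a positive attitude toward CESM" within 3.5 percentage points. It adds "This includes the worst case scenario in which the percentage is 50" per cent, where binomial variance is largest. No confidence level is given, and nothing limits the percentage to women who accept the exam.

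The data come from a narrower group. Biomedical Research, item 2, lists "CESM pre and post surveys for women having CESM procedure only", and item 1 gives the pre-exam survey to women who have agreed to take part. Women enter by two routes. Their previous mammogram is screened from the schedule and "the study nurse will contact the patient to see if they would like to participate in the CESM study". In addition, "study flyers approved by the IRB will be placed at UVa Imaging sites as well as primary care and gynecology offices". The inclusion criteria require every subject to be already scheduled for a screening mammogram. Nothing in this protocol collects data from a woman who declines.

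**The concern.** Whether a woman accepts the exam depends in part on the attitude that the survey measures. The Background suggests that slow uptake of CESM for screening may reflect lower convenience, worry over the IV line or a contrast reaction, or lack of knowledge of the test. The first two are also plausible reasons to refuse the nurse's invitation. Women who hold those views most strongly would then be missing from the percentage. Flyer responders add women for whom there is no count of those who saw the flyer and did not respond.

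The Background and the Risk/Benefit Analysis (item 1) state the aim in terms of the attitudes of patients or women toward screening CESM, without limiting it to women who had the exam. A high approval figure with a narrow margin could be taken as evidence of broad acceptability. The surveyed group cannot supply that evidence alone, and the margin accounts for sampling error only.

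**Working it through.** **1. The plan's own figure.** Inputs from Statistical Considerations, item 3: n = 210, p = 0.50, margin 3.5 points.

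- Standard error = sqrt(0.5 x 0.5 / 210) = 0.0345, or 3.45 points.
- 95% half-width = 1.96 x 3.45 = 6.8 points (exact interval 43.0% to 57.0%, about 7.0 either side).
- 3.5 points corresponds to about 69% confidence. The 80% half-width is 4.4 points and the 90% half-width is 5.7.
- For 3.5 points at 95%: n = (1.96 / 0.035)^2 x 0.25 = 784.

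So the stated margin is about one standard error, and no conventional confidence level reproduces it. Dropout does not explain the difference, since the protocol treats it as negligible ("CESM rates will be negligible due to pre-screening and study procedure involving only one visit").

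**2. Bias from surveying acceptors only.** Let a be the share of invited eligible women who accept, pA the share positive among acceptors and pD the share positive among decliners. The percentage among all invited women is a x pA + (1 - a) x pD. The study observes pA, so

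bias = pA - [a x pA + (1 - a) x pD] = (1 - a) x (pA - pD).

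The protocol gives none of a, pA or pD. The values below are assumptions that show the range. Bias is in percentage points.

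| Acceptance | Gap 5 | Gap 10 | Gap 20 | Gap 30 | Gap at which bias = 3.5 | Gap at which bias = 6.8 |
|---|---|---|---|---|---|---|
| 10% | 4.5 | 9 | 18 | 27 | 3.9 | 7.5 |
| 30% | 3.5 | 7 | 14 | 21 | 5.0 | 9.7 |
| 50% | 2.5 | 5 | 10 | 15 | 7.0 | 13.5 |
| 70% | 1.5 | 3 | 6 | 9 | 11.7 | 22.5 |
| 90% | 0.5 | 1 | 2 | 3 | 35 | 68 |

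The last two columns are the margin divided by (1 - a); for example, 3.5 / 0.5 = 7.0. Across the grid the bias runs from 0.5 to 27 points. It passes the stated margin at modest gaps when half or fewer accept, and only at very large gaps when nearly all accept.

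**The case against.** There is a fair case on the other side, and several parts of it stand.

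- **Size.** A reader might infer that the percentage is biased upward by more than its margin. The protocol does not support that as a fact. At 70% acceptance and a 10-point gap the bias is 3 points, below 3.5. The most that can be said is that it could exceed the margin.
- **Direction.** Item 3 does not say which survey defines a positive attitude. An unpleasant injection could lower attitudes after the exam, so an upward bias is plausible mainly for the pre-exam survey.
- **Wording.** The phrase about general attitudes sits beside a mention of subgroup analyses and may mean only overall rather than by subgroup. The point therefore rests on the unqualified percentage of women.
- **Companion survey.** The Brief Summary describes a separate survey of women with dense breasts at screening, to be compared with women who choose CESM. The project thus already treats acceptors as a distinct group. The survey's content is not visible, so how far it covers general attitudes cannot be judged. It does not correct item 3, which bases its estimate on the 210. The secondary analysis (item 5) also codes unwilling women as 0, but does not say where their data come from.
- **Primary aim.** For willingness to repeat or recommend CESM (item 4), women who had the exam are the right population, and this bias does not arise.
- **Scope.** Stratified reporting and bounds could be left to an analysis plan. A contact log cannot, because no later plan recovers decliners who were never recorded.

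**Conclusion.** The point stands in a limited form. Item 3 names a percentage among women but can deliver only one among women who accepted and underwent CESM. As a figure for women with dense breasts attending for screening it is probably too high on the pre-exam survey. The error could exceed 3.5 points: at an assumed 50% acceptance it does so once acceptors and decliners differ by more than 7 points. Against the 95% half-width of about 6.8, the gap would have to exceed about 13.5 points. The actual size is unknown, because the protocol gives neither acceptance nor the gap.

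A reader might go further and conclude that the study's main results are invalid. They are not: the primary analysis concerns women who had the exam and is unaffected. What is at stake is how the approval percentage and its margin are described, and whether uptake is recorded so that the percentage can be interpreted.

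**What to change.** In Statistical Considerations, item 3:

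- Restate the percentage as that among women who accept and undergo screening CESM.
- Say that the margin covers sampling error only, and give its confidence level: about 6.8 points at 95% for n = 210 and p = 0.5.

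In Biomedical Research, item 1:

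- Have the study nurse, who already makes the calls, log the numbers contacted, eligible, accepting and declining, and record each subject's recruitment route.

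In reporting:

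- Give uptake beside the approval percentage.
- For schedule-contacted women, add a lower bound that counts decliners as not positive, that is a x pA. With an assumed 50% acceptance and 90% approval this would be 0.5 x 0.9 = 45%.
- Show flyer responders separately, since they have no denominator.

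The cost is a revised paragraph, a short log, possibly IRB approval to keep minimal data on decliners, and a narrower stated claim. The sample size and the primary analysis do not change.
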